11.3.3. Safety Population

Safety set will include all procedures/patients defined in the intent-to-treat set.

This set will be the base for the overall study safety assessment.

For study device-specific post-operation safety assessment, only those included in the primary effectiveness set will be used.

Comparability analyses between the two study groups will be conducted on the Intent-to-Treat analysis set.

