6.4. Study Endpoints

6.4.1. Primary Effectiveness Endpoint

The primary effectiveness endpoint is procedural success defined as creation of the parenchymal tract between the hepatic vein and an intrahepatic branch of the portal vein and confirmed by portogram (CO₂/contrast).

Failure to create the parenchymal tract between the hepatic vein and the portal vein with the randomized assignment will be considered a treatment failure. A minimum of 5 needle passes should be attempted before selecting the alternative set.

In the event of a treatment failure, the physician will follow their standard of care procedures and/or use another commercially available product. The patient should be followed in the study through hospital discharge for adverse event monitoring.

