6.4.3. Secondary and Exploratory Endpoints

The secondary and exploratory endpoints of this clinical study are outlined in **Table 5**.

TABLE 5. OVERVIEW OF SECONDARY AND EXPLORATORY ENDPOINTS

Endpoint	Description / Definition
Secondary Endpoints	
Portal Vein Access (PVA) time	Time (in minutes) from initial needle throw to portal vein access as confirmed by portogram
Technical success	Creation of a shunt (stent bridging) between the portal and systemic veins
Number of needle passes	Count of needle throws between the hepatic and portal vein to create the parenchymal tract
Procedure duration	Interval (in minutes) from first jugular access for TIPS creation to removal of catheters from subject
Fluoroscopy time	Measured in minutes
Device-related complications	Incidence of complications related to the device as judged by the Principal Investigator
Exploratory Endpoints	

Change in MELD score	Change in score from Screening to Day 30
Change in Child-Pugh score	
Radiation dosage	Measured in air kerma (mGy)
Contrast volume used	Measured in mL
Length of Hospital Stay	Measured in days
Number of ICU days	Measured in days
Change in HPVG	Measured in mm Hg

MELD = Model for End-Stage Liver Disease; ICU = Intensive Care Unit; HPVG = Hepatic Venous Pressure

Gradient

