6.7. Study Duration

The study enrollment period is anticipated to take approximately 6 months. Enrolled subjects are followed for 30 days from the TIPS procedure requiring individual subject participation for approximately 1 month.

Upon completion of all enrolled subjects, study closure, including data analysis and preparation of the clinical study report, is estimated to take up to an additional 6 months.

Total study duration is expected to be approximately 13 months.

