11.3. Analysis Sets

11.3.1. Intent-to-Treat Set

The intent-to-treat set will include all procedures/patients with an attempted TIP procedure using a study device regardless it is successful, or an alternative device is needed.

This set will be the base for assessment of technical success rate and overall procedure success rate, as well as overall device safety.

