11.3.2. Primary Effectiveness Set

The primary effectiveness set will include procedures/patients who have a successful procedure with only a study device (i.e., no need of an alternative device).

This set will be the base for assessment of cannulation time, fluoroscopy time, procedure duration, as well as other device-specific outcomes.

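### Device-specific safety is assessed only in subjects whose access succeeded with the assigned set alone, so treatment failures and switches drop out of it

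*Combined protocol and SAP*

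**What the plan says.** Section 11.3.3 equates the safety set with the ITT set and uses it for overall study safety. It then makes an exception: "For study device-specific post-operation safety assessment, only those included in the primary effectiveness set will be used".

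Section 11.3.2 defines the restricted set: "The primary effectiveness set will include procedures/patients who have a successful procedure with only a study device (i.e., no need of an alternative device"). The same section gives that set a broad remit: "This set will be the base for assessment of cannulation time, fluoroscopy time, procedure duration, as well as other device-specific outcomes". Section 11.3.1 says of the ITT set: "This set will be the base for assessment of technical success rate and overall procedure success rate, as well as overall device safety".

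Table 5 in Section 6.4.3 lists device-related complications as a secondary endpoint, described as "Incidence of complications related to the device as judged by the Principal Investigator". It names no analysis set for it.

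Section 6.4.1 classes inability to create the tract with the randomized set as treatment failure. On switching it says: "A minimum of 5 needle passes should be attempted before selecting the alternative set". On follow-up of these subjects it says: "The patient should be followed in the study through hospital discharge for adverse event monitoring". Section 6.7, by contrast, says: "Enrolled subjects are followed for 30 days from the TIPS procedure".

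**The concern.** Membership of the restricted set is decided after randomization and after puncture, by an outcome close to the primary effectiveness endpoint. The subjects left out were exposed to the assigned set, normally for at least five passes. Section 3.1 says that arterial, biliary and extracapsular injury can occur while portal access is being attempted, and that the potential for such complications may rise with the number of passes. A perforation that ends the attempt could make the subject a failure and so remove that same event from the device-specific rate.

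Two gaps make this worse. Device-related complications could fall under overall device safety (Section 11.3.1, ITT) or under other device-specific outcomes (Section 11.3.2, successes only), so one data set can give two answers in an open-label study. And post-operation is not defined. Section 8.3 records events both during and after the procedure, so it is unclear whether intraprocedural punctures count.

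Section 3.3 says the study is to supply clinical data for the initial CE Mark application. A device complication rate offered for that purpose should not be conditional on the device having worked.

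**Working it through.** The plan gives no failure rate, complication rate among failures, alpha, power or margin, so there is no planned figure to reproduce. The check has two parts.

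**1. Reading the rules together**

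- Section 11.3.3: device-specific post-operation safety uses the primary effectiveness set only.
- Section 11.3.2: that set requires success and no alternative device.
- Section 6.4.1: failure and switching occur during the procedure, after randomization.
- No other section returns failures or switches to the device-specific assessment. They remain only in the ITT-based analyses of Sections 11.3.1 and 11.3.3.

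**2. Illustration of size**

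Inputs: 30 subjects per arm (Section 6.6). The all-exposed rate is r = 3.6%, the puncture-complication incidence cited for the Cook sets in Section 3.2, assumed here for either arm. The failure-or-switch share f and the ratio RR (risk in failures divided by risk in successes) are assumptions, varied over 5% to 20% and 1 to 5.

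Expected exclusions per arm are 30 × f, and the chance of at least one is 1 − (1 − f)^30:

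- f = 5%: 1.5 subjects, 78.5%
- f = 10%: 3 subjects, 95.8%
- f = 20%: 6 subjects, 99.9%

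Since r = (1 − f) × (risk in successes) + f × RR × (risk in successes):

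- restricted rate = r / (1 − f + f × RR)
- share of events dropped = f × RR / (1 − f + f × RR)

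For f = 10% and RR = 3, the denominator is 0.90 + 0.30 = 1.20. The restricted rate is 3.6% / 1.20 = 3.0%, and the dropped share is 0.30 / 1.20 = 25%.

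| f | RR | Restricted rate | Events dropped |
|---|---|---|---|
| 5% | 1 | 3.60% | 5.0% |
| 5% | 3 | 3.27% | 13.6% |
| 5% | 5 | 3.00% | 20.8% |
| 10% | 1 | 3.60% | 10.0% |
| 10% | 3 | 3.00% | 25.0% |
| 10% | 5 | 2.57% | 35.7% |
| 20% | 1 | 3.60% | 20.0% |
| 20% | 3 | 2.57% | 42.9% |
| 20% | 5 | 2.00% | 55.6% |

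At RR = 1 events are lost but the rate is not biased.

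Expected events per arm are 30 × 0.036 = 1.08. Those dropped range from 1.08 × 0.05 = 0.05 to 1.08 × 0.556 = 0.60.

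**Between arms, with failures of 5% and 20%**

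- *Equal all-exposed rates of 3.6%.* At RR = 3 the restricted rates are 3.6/1.1 = 3.27% and 3.6/1.4 = 2.57%, a spurious 0.70-point advantage for the arm that fails more. The gap is 0 at RR = 1 and 3.0% − 2.0% = 1.0 point at RR = 5.
- *Equal risks within each stratum, 3% after success and 15% after failure.* The all-exposed rates are 0.95 × 3 + 0.05 × 15 = 3.6% and 0.80 × 3 + 0.20 × 15 = 5.4%, a true difference of 1.8 points. Both restricted rates are 3.0%, so the difference disappears.

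**The case against.** The best defence is that the main safety results are protected. Overall device safety and overall study safety are on the ITT set, the primary safety composite is not assigned to the restricted set, and no formal hypothesis is tested. This stands, and it limits the consequence. It does not tell a reader which denominator applies to device-related complications.

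The restriction may also have a sensible purpose, though the plan does not state one: after exposure to two manufacturers' sets, a later event is hard to attribute. But the rule also removes failures in whom no second set was used, where that difficulty does not arise. For switched subjects, attribution and separate listing deal with it without deleting anyone.

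The illustration is open to challenge. The 3.6% anchor concerns puncture complications and may not apply if intraprocedural events are not covered. Section 3.1 says only that risk may rise with passes and does not compare failures with successes. Section 3.2 reports 100% technical success in 15 retrospective Scorpion X cases, a related but different outcome. Zero failures in 15 is compatible with a rate up to about 18% (one-sided 95% bound, 1 − 0.05^(1/15)), so it neither excludes failures nor supports 20%. The spurious advantage also needs equal all-exposed rates, which forces risk among successes to differ between arms. With equal stratum risks the failing arm does not look safer, but its excess is hidden, which still favours it.

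Finally, the effects are small beside sampling error: the standard error of a difference at 3.6% with 30 per arm is √(2 × 0.036 × 0.964 / 30), about 4.8 points. That is fair. Yet with about one event expected per arm, dropping a single subject can turn an observed event into none.

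**Conclusion.** The concern holds. As written, the device-specific post-operation safety assessment is conditioned on a post-randomization outcome and leaves out exposed subjects who failed or switched. That much follows from the text alone.

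The size is not known. The assumed ranges give a restricted rate of 2.0% to 3.6% against 3.6% in all exposed subjects, with 0.05 to 0.60 expected events dropped per arm of 30. The rate is biased downwards only if failures carry more risk than successes, which the protocol's background suggests but no figure in it shows.

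Within safety, the defect is confined to this assessment and to whatever endpoint is assigned to it. With ITT-based overall safety intact and comparisons exploratory, this is something that should be fixed and not a threat to the study as a whole.

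**What to change.** - **Section 11.3.3:** base device-specific safety, including device-related complications, on the ITT/safety set by randomized arm, whether or not access succeeded or another set was used. Define post-operation and say whether intraprocedural events are included.
- **Section 11.3.2:** exclude safety outcomes from the device-specific outcomes assigned to the restricted set. Keep the success-only safety analysis, labelled supportive.
- **Table 5:** name the analysis set for device-related complications.
- **Subjects exposed to two sets:** record which set each event is attributed to and list these subjects separately. Sections 8.3 and 10.5.1 already collect use of an alternative set and causality to device or procedure, so at most one field is needed if the eCRF does not already hold it.
- **Follow-up:** reconcile Section 6.4.1 (treatment failures followed through discharge) with Sections 6.7 and 8.1 (30 days). This is a separate inconsistency, but until it is settled the event window for the restored subjects is unclear.

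The cost is two sentences in the statistical section, one endpoint assignment, possibly one eCRF field, and the follow-up wording. The reported device complication rate may be slightly less favourable, and events after a switch will remain harder to attribute.

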11.4. Missing Data

Missing data will not be imputed unless otherwise specified.

For categorical variable, if unknown and missing data may be presented as a separate category and the denominator might include unknown and missing category where deems appropriate.

11.5. Interim Analysis

One interim analysis will be conducted when the first 15 cases in each group complete the study procedure. The main purpose of the interim analysis is to more accurately fine tune the study design based on study-specific data. The interim analysis will focus on the impact of the primary imaging techniques on procedural success. If imaging technique is a significant factor, stratified randomization by primary imaging techniques will apply for future included participants. Justification for multiplicity is unnecessary as no formal statistical hypothesis will be tested.

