7.7. Randomization

Randomization will occur after an eligible subject has signed the ICF and prior to initiation of the TIPS procedure. Subjects will be randomly assigned at a 1:1 ratio into one of the two study groups (Scorpion or Cook) via a centralized randomization service.

Once the randomization assignment is received, the physician will determine the model he/she wants to use based on preference, training, and the subject case before beginning the procedure.

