8.3. TIPS Procedure (Day 0)

The TIPS procedure will be completed in a clinical setting with adequate angiographic equipment and institutional facilities, physiologic monitoring equipment, and support personnel.

Transjugular liver access will be obtained using either the Scorpion set or Cook set per randomization assignment and physician choice of model. The procedure will be performed in accordance with the Scorpion IFU or the Cook IFU. Refer to the current IFU included with the device for techniques and methods for pre-procedure preparation and directions for use. The specific model and treatment details (e.g., access site, access side, stent, etc.) will be determined by the physician based on the condition of the subject.

A minimum of 5 needle passes should be attempted with the initial device assigned through randomization before selecting the alternative manufacturer set. If an alternative manufacturer set is selected, the information will be recorded as part of the study records.

The following procedure data are to be collected and recorded in the subject's medical record or other applicable source documents which will be reported on the appropriate eCRF:

Jugular access site
Number of needle passes
Hepatic vein used for access
Access device used
Portal vein access site
Imaging used
Alternate access sites/techniques used
Sheath used
Stent used, dilated to what size
Pressure gradient measurements: pre- and post-delivery of stent
Presence of residual varices
Adverse events (during and post procedure)
Record Concomitant Medications (only rifaximin, lactulose, and medications which are an anticoagulant, antiplatelet, or diuretic will be recorded)

A portogram must be obtained to confirm creation of the parenchymal tract between the hepatic vein and an intrahepatic branch of the portal vein upon portal vein access and following stent deployment.

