11.1.2. Exploratory Comparisons

Between-group comparisons will be conducted using Student's t-test for continuous variables and Pearson's Chi-square test for categorical variables. Comparability analysis between two study groups will be first conducted based on demographic and clinical parameters.

Appropriate statistical methods will be employed to explore the correlation and impact of the unbalanced baseline variable, if any, on the study results. When necessary, advanced statistical method such as mixed linear models will be employed to justify the impact.

When sample size permits, the outcomes will be reported for sub-groups such as by gender, age group (≤ 50 years vs > 50 years), type of image used, or operation experience.

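### The interim look and the imaging subgroup use a guidance variable that is undefined and recorded only after the open-label assignment is known; a planned value should be recorded before assignment

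*Combined protocol and SAP*

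**What the plan says.** Section 11.5 sets the timing: "One interim analysis will be conducted when the first 15 cases in each group complete the study procedure". The question follows: "The interim analysis will focus on the impact of the primary imaging techniques on procedural success". The consequence is conditional: "If imaging technique is a significant factor, stratified randomization by primary imaging techniques will apply for future included participants". No test or significance level is given. Imaging technique is the only stratification factor named anywhere. Section 7.7 describes plain 1:1 allocation, and section 13.10 lists stratified randomisation as a bias control only if it applies after the interim analysis.

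On the order of events, section 7.7 says "Randomization will occur after an eligible subject has signed the ICF and prior to initiation of the TIPS procedure", and then "Once the randomization assignment is received, the physician will determine the model he/she wants to use based on preference, training, and the subject case". Section 7.8 confirms that the study is open-label.

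Guidance imaging appears once in the data collection, as the *Imaging used* item in the Day 0 procedure list of section 8.3. The same list has a separate item, "Alternate access sites/techniques used". The screening list in section 8.2 and the Screening column of Table 6 contain CT or MRI and echocardiography. These assess vascular patency, liver masses and cardiopulmonary status; they do not record how the portal vein puncture will be guided.

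Section 11.1.2 plans to report outcomes, when sample size permits, for "sub-groups such as by gender, age group (≤ 50 years vs > 50 years), type of image used, or operation experience".

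**The concern.** A factor used to stratify, or to form subgroups within which randomised arms are compared, should be fixed before the assignment is known. Here the only required record of guidance is made during or after the procedure, by an operator who knows which set was assigned. Sections 6.4.1 and 8.3 ask for at least five needle passes before the set is changed, but the protocol has no rule about changing guidance between passes. It also does not say which technique counts as primary when more than one is used.

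Two things are at stake. First, if difficult cases move between imaging categories because they are difficult, an imaging effect can appear where none exists, or a real one can be hidden, and section 11.5 changes the design on that result. Second, if guidance is chosen in light of the assigned set, comparing Scorpion with Cook within an imaging type is no longer a randomised comparison. The sponsor has reason to care about the answer: section 3.2 cites a mean time to portal access of 46 minutes with conventional fluoroscopy against 31 minutes with intravascular ultrasound.

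There is also a mismatch inside the plan. Stratified allocation can only use a value declared before randomisation. The interim analysis has, as a required item, only the value recorded at the procedure. The plan does not link the two.

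**Working it through.** The plan gives no success rate, significance level or switching rate, so there is no figure of its own to reproduce. The order of events can be checked directly; the size can only be illustrated.

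**1. Order of events.** Consent, then randomisation, then assignment known to the operator (7.7, 7.8), then procedure, then *Imaging used* recorded (8.3). No item in 7.4, 7.7, 8.2 or Table 6 asks for planned guidance. The required imaging variable is therefore post-assignment for every subject, including the first 30.

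**2. Size of a false gap.** Assumptions: half of cases are planned under fluoroscopy and half under ultrasound; failure is f in both, so imaging has no effect; a share s of failing fluoroscopy cases is recorded as ultrasound.

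- Recorded fluoroscopy failure = 0.5f(1−s) / (0.5 − 0.5fs)
- Recorded ultrasound failure = (0.5f + 0.5fs) / (0.5 + 0.5fs)
- f = 0.10, s = 0.50: 0.025/0.475 = 5.3% and 0.075/0.525 = 14.3%, a gap of 9.0 points
- f = 0.05, s = 0.25: 3.8% and 6.2%, a gap of 2.4 points
- f = 0.15, s = 0.75: 4.2% and 23.6%, a gap of 19.4 points

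In patients, with 15 planned under fluoroscopy, the expected number moved is 15fs: 15 × 0.10 × 0.50 = 0.75 in the first case and 15 × 0.15 × 0.75 = 1.7 in the last.

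**3. Sensitivity to direction.** If every converted case in the first example is rescued, recorded ultrasound failure falls to 0.05/0.525 = 9.5% against 5.3%, so the gap shrinks to 4.3 points (9.52 − 5.26). If ultrasound is truly better (5% against 10% failure) and half of the failing fluoroscopy cases are relabelled without rescue, the recorded figures are (0.025 + 0.025)/0.525 = 9.5% for ultrasound and 5.3% for fluoroscopy: a real benefit appears as harm. Conversions from ultrasound to fluoroscopy would reverse the signs.

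**4. Effect on the decision to stratify.** Assumptions: 15 and 15 planned, Pearson's test (named in 11.1.2) at an assumed 0.05 level. Simulating the model of step 2, the false-trigger rate for f = 0.10 is 6.8% with s = 0.50, against between 2.4% and 2.5% with no conversion. Over the range in step 2 it runs from 0.7% to 26%.

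**5. A different mechanism.** A second simulation let difficult cases switch technique whatever their outcome, again with no true imaging effect (30 cases; 20% or 30% difficult; success 98% in easy cases and 70% or 50% in difficult ones; half or all of the difficult cases planned under one technique switch). The recorded technique gave spurious gaps of 4.5 to 22.2 points and false signals in 2.3% to 23.4% of runs. The planned technique gave no gap and 1.9% to 4.8%. In four of the six switching scenarios the false-signal rate stayed at or below 5.2%.

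**The case against.** The strongest reply is that the documents do not show guidance changing for either reason. The sentence quoted from section 7.7 concerns the model of the set, not imaging. The discretion sentence in section 8.3 names access site, access side and stent, and does not name imaging. The item for alternate sites and techniques may refer to access only; if it does cover imaging, conversions are recorded separately and need not overwrite the primary technique. "Primary" could also mean the technique the operator started with. All of this stands. It makes the switching an inference from what the plan permits, and it makes the missing definition part of the problem.

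A reader might infer that the plan stratifies on a post-randomisation variable. It does not: stratification is conditional, and if triggered it would have to use a technique declared before assignment. A reader might also infer that no pre-assignment value can exist for the first 30 cases. That is too absolute, because the case report form and the specification of the randomisation service are not among these documents. What can be said is that the protocol does not require one.

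The model in step 2 relabels only failing cases, and step 3 shows that the gap shrinks when conversions are rescued. The consequence is also limited. A wrong trigger changes only how the remaining 30 or so subjects are allocated, no formal hypothesis is tested, and subgroups are reported only when numbers permit.

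What remains is that the plan, followed as written, has no required variable that separates intended guidance from guidance adapted during the case, and it uses guidance both to decide on a design change and to form a subgroup.

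**Conclusion.** The point holds as a gap in definition and timing. The interim analysis and the imaging subgroup rest on a guidance variable that is undefined and recorded after a known assignment, and any later stratification would have to use a different, planned value.

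The size is unknown. In the illustrations the spurious gap ranges from about 2 to 22 percentage points, but in a 30-case look this may reflect a shift of only one or two patients. The chance of a false trigger ranges from below 1% to about 26%, with the high values arising only under strong assumptions. All failure rates, switching rates, the even split by technique and the 0.05 level are assumptions.

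The documents do not support the stronger conclusions that device or difficulty does alter guidance in this trial, or that the main comparison is compromised. Scorpion versus Cook overall stays randomised whichever way the interim decision falls. This is a cheap improvement worth making, not a flaw that undermines the study.

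**What to change.** Add one field, planned primary imaging guidance, completed in the central randomisation system before the assignment is released, from the first subject. Define primary in the protocol, for example as the technique intended for the first needle pass, and say how a plan with more than one technique is coded. Use the planned value in the interim analysis (11.5), in any stratification that follows and in the imaging subgroup (11.1.2). Keep *Imaging used* in 8.3 as a descriptive item reported by arm, with any change from plan recorded. State in 11.5 the test and level that define a significant factor.

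The cost is one extra field and short wording changes in sections 7.7, 8.2, 11.1.2 and 11.5. Operators declare a plan but remain free to change guidance during the procedure. The field should be in place before enrolment starts, because a plan reconstructed afterwards would be informed by the assignment and the outcome.
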